6.6.1 Dose modification criteria

6.6.1.1 General guidelines for adagrasib (Part-3)

The following are the general guidelines for withholding, resumption or re-challenge of treatment with adagrasib:

- following adagrasib dose reduction and control of an AE, re-challenge at a higher adagrasib dose may be permitted after discussion with the Sponsor;

- if resumption of dosing for adagrasib is delayed for ≥ 14 days due to an AE that is at least suspected to be attributable to study treatment, then resumption at a reduced dose should be considered;
- if treatment with adagrasib is withheld for ≥ 22 consecutive days, then permanent discontinuation from treatment with one or both agents should be considered; and
- if a treatment-related AE recurs despite dose reduction of adagrasib to the lowest dose anticipated, then permanent discontinuation from study treatment should be considered, unless after discussion with the Sponsor it is considered to be in the best interest of the participant to continue.

Treatment interruptions and modification guidelines are provided in Appendix 9 ([Section 10.9](#)).

Additional guidelines for adagrasib:

Hepatic Toxicities

Hepatic toxicities that are considered to be causally related to adagrasib should initially be managed with treatment interruption of one or both study drugs as outlined in [Table 27](#). Evaluations for confounding factors (eg, cholestasis, metastasis, or viral infection) should be performed as clinically indicated, and more frequent monitoring of a hepatic panel (including AST, ALT, alkaline phosphatase, and bilirubin) should be considered for those participants with transaminase increases. Following resolution of toxicity to the specified degree, dose reduction of adagrasib should be implemented.

Other Laboratory Investigation-Based Toxicities

Other laboratory investigation-based toxicities that are considered to be causally related to adagrasib should initially be managed with treatment interruption of adagrasib as outlined in [Table 27](#). Following resolution of toxicity to the specified degree, dose reduction of adagrasib should be implemented.

Cardiac Toxicities

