- Concurrent increase in ALT and AST $>3 \times$ ULN AND total bilirubin $>2 \times$ ULN or INR >1.5 ULN in the absence of cholestasis and other causes (eg, viral hepatitis, other pre-existing or acute liver disease, or another drug capable of the observed injury), which may indicate severe drug-induced liver injury (possible Hy's law). Study drug should be withheld until AST, ALT, return to $<2 \times$ ULN and total bilirubin returns to $<1.5 \times$ ULN.
- Other project specific AESI(s)
 - QT (corrected or uncorrected) >480 msec or increased from baseline >60 msec (see [Section 7.1.1](#) QT prolongation management advice)
 - Thrombocytopenia Grade ≥ 3 or any grade if associated with clinically significant bleeding (see [Section 6.6.1.8](#) for hemorrhage management guidelines)

- Edema, including generalized/peripheral edema or facial/periorbital edema (see [Section 6.6.1.12](#) for edema management guidelines)
- All protocol defined potential or IMP related DLTs are considered as AESI, regardless of the cycle of occurrence (ie, after Cycle 1 in both escalation and expansion phases)

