Other screening tests	
Coagulation test to include prothrombin time (PT)/international normalized ration (INR) and aPTT (or partial thromboplastin time)
 
Follicle-stimulating hormone and estradiol (as needed in women of non-childbearing potential only)^c
 
Highly sensitive blood or urine human chorionic gonadotropin (hCG) pregnancy test (as needed for women of childbearing potential)^b
 
Serology: hepatitis B surface antigen (HBsAg), hepatitis B core antibody (HBcAb), and hepatitis C virus antibody. If hepatitis C virus antibody is positive, then obtain hepatitis-C RNA
 
The results of each test must be entered into the case report form (CRF).

NOTES :

- a Concurrent elevation of AST or ALT >3 x ULN AND total bilirubin >2 x ULN or INR >1.5 in the absence of cholestasis and other causes (eg, viral hepatitis, other pre-existing or acute liver disease, or another drug capable of the observed injury), which may indicate severe drug-induced liver injury (possible Hy's law case). All events with the defined biochemical abnormalities must be reported as an SAE; and study medications should be permanently discontinued.
- b Local urine testing will be standard for the protocol unless blood testing is required by local regulation or IRB/IEC. For screening a blood test is required.
- c See Appendix 4 ([Section 10.4](#)).

Investigators must document their review of each laboratory safety report.

10.3 APPENDIX 3: ADVERSE EVENTS: DEFINITIONS AND PROCEDURES FOR RECORDING, EVALUATING, FOLLOW-UP, AND REPORTING

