Hepatitis, liver function test abnormalities (AST, ALT, and/or total bilirubin)	
Grade 1: Continue both study drugs at current doses.
 
Grade 2: In Part-1, 2, and 4, continue SAR442720 and withhold pembrolizumab until adverse reactions recover to Grade 0 to 1
 
In Part-3, continue SAR442720 and reduce adagrasib one dose level.
 
Grade 3: Rule out other causes such as metastatic liver disease, concomitant drugs, infection, etc. Withhold both study drugs until improves < Grade 1, then dose reduce SAR442720 and adagrasib one dose level (in Part-3) and resume pembrolizumab at the same dose (Part-1, 2 and 4). If AE does not improve or recurs, dose reduce another dose level of SAR442720. No dose modification required for isolated GGT. In Part-1, 2, and 4 hold SAR442720; if no improvement in LFTs after SAR442720, withhold pembrolizumab as well. If Grade ≥ 3 with AST or ALT occurs, permanently discontinue both study drugs.
 
In case of liver metastasis with baseline Grade 2 elevation of AST or ALT, hepatitis with AST or ALT increases $\geq 50\%$ and lasts ≥ 1 week: Permanently discontinue pembrolizumab. Action with SAR442720 or adagrasib should be discussed with the Medical Monitor.
 
Grade 4: see general Grade 4 non-heme AEs. In Part-1, 2, and 4 hold both SAR442720 and pembrolizumab. If resolves, restart both medications, SAR442720 at reduced dose (pembrolizumab dose reduction is not allowed). If no improvement to < Grade 1 within 4 weeks, permanently discontinue both drugs.
 
In Part-3 permanently discontinue both study drugs. Concurrent treatment-emergent / treatment related elevation of AST or ALT $> 3 \times$ ULN AND total bilirubin $> 2 \times$ ULN or INR > 1.5 in the absence of cholestasis and other causes (eg, viral hepatitis, other pre-existing or acute liver disease, or another drug capable of the observed injury), which may indicate severe drug-induced liver injury (possible Hy's law case). Both medications should be permanently discontinued.
 
If liver injury is due to other causes such as viral hepatitis, acute liver disease, or another drug capable of liver injury, evaluate the extent of liver injury (eg, albumin level, PTT, INR etc) and if considered to be severe, discontinue both medications.

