Endocrinopathies (applies to Part-1, 2, 4)	
Grade 2 adrenal insufficiency and hypophysitis: continue SAR442720 and withhold pembrolizumab until controlled by hormone replacement.
 
Grade 3 or 4 adrenal insufficiency or symptomatic hypophysitis, Type 1 diabetes associated with Grade \geq3 hyperglycemia (glucose >250 mg/dL or >13.9 mmol/L) or associated with ketoacidosis.
 
Hyperthyroidism Grade \geq3: continue SAR442720 and withhold pembrolizumab until adverse reactions recover to Grades 0 to 1.
 
For patients with Grade 3 or Grade 4 endocrinopathies that improved to Grade 2 or lower and controlled with hormone replacement, if indicated, continuation of pembrolizumab may be considered after corticosteroid taper, if needed. Otherwise pembrolizumab treatment should be discontinued.
 
Hypothyroidism may be managed with replacement therapy without treatment interruption.

Other immune-related adverse reactions (applies to Part-1, 2, 4)	
Based on the severity and type of reaction (Grade 2 or Grade 3): Continue SAR442720 and withhold pembrolizumab until adverse reactions recover to Grades 0 to 1. SAR442720 may need to be withheld temporarily depending on the individual case assessment.
 
Grade 3 or Grade 4 myocarditis; Grades 3 or Grade 4 encephalitis; Grade 3 or Grade 4 Guillain-Barre syndrome and all Grade 4 or recurrent Grade 3 immune related adverse reactions: Permanently discontinue both study drugs.
 
Consult with Medical Monitor as necessary.

Pembrolizumab Infusion-related reactions (applies to Part-1, 2, 4)	Grades 3 or Grade 4 infusion related reactions: Permanently discontinue pembrolizumab.

AE	Action
Pneumonitis	Part-1, 2, and 4: For Grade 2 hold both drugs and re-start when toxicity resolves to \leq Grade 1 For Grades 3 and 4 – Permanently discontinue treatment with pembrolizumab and withhold SAR442720. However, once recovered to \leq Grade 1, treatment with SAR442720 may be re-started at a lower dose. In Part-3; Grade 1 consider reducing adagrasib by one dose level. Grade 2 hold adagrasib until \leq Grade 1 or return to baseline. If resumed, decrease by one dose level lower. For Grade 2 recurrent or Grade 3 pneumonitis, discontinue both study drugs.

"Both study drugs" refer to either SAR442720 and pembrolizumab (in Part-1, 2, and 4) or SAR442720 and adagrasib (in Part-3)

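### Possible Hy's law cases are told both to withhold until recovery and to stop for good, and Table 27 gives two incompatible actions for Grade 3 or higher AST/ALT

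*Protocol*

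**What the plan says.** **Possible Hy's law.** Three places give an action.

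- Section 8.3.6 (adverse events of special interest, AESI): "Study drug should be withheld until AST, ALT, return to" below 2 × ULN, with total bilirubin below 1.5 × ULN. The trigger is a concurrent rise in ALT *and* AST.
- Appendix 2, Table 22, note a: "All events with the defined biochemical abnormalities must be reported as an SAE; and study medications should be permanently discontinued". The trigger is AST *or* ALT.
- Appendix 9, Table 27, liver row: "Both medications should be permanently discontinued". The trigger is again AST *or* ALT, as it is in the DLT criteria of Section 4.1.1.

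**Grade 3 or higher AST/ALT.** The Table 27 liver row covers AST, ALT and/or total bilirubin.

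- Its Grade 3 paragraph withholds both drugs until improvement to below Grade 1, "then dose reduce SAR442720 and adagrasib one dose level (in Part-3) and resume pembrolizumab at the same dose (Part-1, 2 and 4".
- The same paragraph ends with a sentence on Grade 3 or higher: "with AST or ALT occurs, permanently discontinue both study drugs".
- At Grade 4 in Parts 1, 2 and 4 the row says: "If resolves, restart both medications, SAR442720 at reduced dose (pembrolizumab dose reduction is not allowed". In Part-3, Grade 4 is a permanent stop.
- The table footnote says that the term for both drugs is to "refer to either SAR442720 and pembrolizumab (in Part-1, 2, and 4) or SAR442720 and adagrasib (in Part-3".
- Section 6.6.1.1, for Part-3: "Hepatic toxicities that are considered to be causally related to adagrasib should initially be managed with treatment interruption of one or both study drugs", followed by an adagrasib dose reduction once the toxicity resolves.

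**The concern.** A possible Hy's law case is the clearest signal of severe drug-induced liver injury that a trial can meet. An investigator who reads only the AESI section finds recovery thresholds, and such thresholds serve little purpose unless drug may then be given again. An investigator who reads Appendix 2 or Table 27 stops for good. Two sites could therefore manage the same participant in opposite ways, and one of them would re-expose the participant.

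The Table 27 conflict is less acute but covers a wider set of events. An isolated Grade 3 ALT rise is either an interruption or the end of treatment, depending on which sentence of one paragraph the site follows. All three drugs have a liver signal: ALT increased in 16.2% and AST increased in 14.7% for adagrasib (Section 2.3.1.4), AST increase in 20.4% for SAR442720 (Section 2.3.1.1), and immune-mediated hepatitis for pembrolizumab (Section 2.3.1.2). The percentages are for all grades, and the SAR442720 figure is regardless of relationship.

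**Working it through.** **Step 1. Hy's law texts compared.** One place says withhold until recovery and two say stop permanently. The statement in Appendix 9 that its recommendations are guidelines subject to clinical judgment applies to Tables 26 and 27. It does not cover Section 8.3.6 or Appendix 2, so it cannot reconcile them. The triggers differ too. A participant with ALT above 3 × ULN, AST at or below 3 × ULN and bilirubin above 2 × ULN meets Section 4.1.1, Appendix 2 and Table 27, but not the liver bullet of Section 8.3.6.

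**Step 2. The Table 27 liver row, by part.**

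- Parts 1, 2 and 4, Grade 3: resume pembrolizumab, against a permanent stop of both drugs.
- Parts 1, 2 and 4, Grade 4: restart both drugs if resolved, against the same stop sentence, which covers Grade 3 or higher.
- Part-3, Grade 3: reduce both drugs after recovery (also Section 6.6.1.1), against the stop sentence if the footnote carries it into Part-3.

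Limiting withhold-and-resume to bilirubin would reconcile the row, but nothing in it says so. The Appendix 9 rule to follow the most conservative advice is for several adverse events with different recommendations, not one event with two.

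**Step 3. Conditional check: could the choice change DLT status in Part-3A?** Section 4.1.1 makes Grade 3 AST/ALT a DLT only if it lasts more than 5 days. Separately, toxicity that prevents delivery of 66.7% of adagrasib is a DLT, with no recovery exception in that sentence.

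Inputs: adagrasib 2 × 21 = 42 doses; SAR442720 on Days 1, 2, 8, 9, 15 and 16 = 6 doses. The plan's own threshold reproduces: 28/42 = 66.7% (Table 20).

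For a related rise found before dosing on Day k:

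- Permanent stop delivers 2(k − 1) of 42 adagrasib doses. Day 8: 14/42 = 33.3%, with 2/6 SAR442720 doses, so a DLT. Day 14: 26/42 = 61.9%, a DLT. Day 15: 28/42 = 66.7%, on the threshold and not a DLT.
- A hold of h days delivers 42 − 2h. Five days: 32/42 = 76.2%, and 4/6 SAR442720 doses after a Day 8 onset, so not a DLT. Seven days: 28/42 = 66.7%, the limit.

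The same five-day hold from Day 8, counted in mg with a one-level adagrasib reduction:

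- 600 to 400 mg: (14 × 600 + 18 × 400)/(42 × 600) = 15,600/25,200 = 61.9%.
- 400 to 200 mg (an assumed level; none below 400 mg is defined): (14 × 400 + 18 × 200)/(42 × 400) = 9,200/16,800 = 54.8%.

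Both are below 66.7%, so in this example the two rules then give the same answer.

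**The case against.** **Hy's law.** Section 8.3.6 defines and reports AESIs and contains no explicit instruction to restart. Two other places, one of them the dose-modification table, require a permanent stop. These events are also DLTs in their own right under Section 4.1.1, so no endpoint changes. The *and*/*or* mismatch is unlikely to lose reports, because Appendix 2 makes the event an SAE and Section 8.3.6 makes all DLT-type events AESIs. All of this is fair and limits the consequence. It does not remove an instruction in the body text that points the other way on re-exposure.

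**Reach into Part-3.** The stop sentence directly follows one limited to Parts 1, 2 and 4. If it already applied in Part-3, the separate Part-3 permanent stop at Grade 4 would be redundant for AST/ALT. The footnote defines a term; it does not assign the sentence to a part. This stands: the Part-3 conflict is arguable, not established. It leaves the conflict in Parts 1, 2 and 4 untouched.

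**The stronger reading.** A reader might infer that the contradiction decides whether a transient Grade 3 ALT rise counts as a DLT in Part-3A, and so steers dose escalation. The documents do not support that as a general statement:

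- It needs the stop sentence to apply in Part-3.
- Restart needs improvement to below Grade 1, not merely leaving Grade 3. The next scheduled laboratory visit after Day 8 is Day 15, and a restart then gives exactly 28/42.
- The contrast is gone from Day 15, and in the Day 8 example it is gone by mg.
- Section 6.6 bars Cycle 1 dose modifications in escalation cohorts unless a DLT has occurred, which read literally bars the hold as well.
- Section 4.1 requires 80% of both drugs for DLT evaluability in Part-3A. The hold case (76.2% and 66.7%) would then be non-evaluable and replaced, rather than counted as free of DLT.
- The mTPI2 target and interval are redacted, and the Sponsor and recruiting Investigators confirm each DLT.

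**Conclusion.** Both contradictions are in the current text. The Hy's law conflict is the main point: one place implies resumption after recovery, and two require a permanent stop. The AST/ALT conflict in Table 27 is certain for Parts 1, 2 and 4 and arguable for Part-3.

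The Part-3A DLT effect is a secondary note. If the stop sentence applies there and delivery is counted in doses, a related Grade 3 ALT rise found before Day 15 becomes a DLT through the delivery criterion. A hold of at most 7 days with recovery to below Grade 1 does not.

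Severity is moderate. The documents give no rate for Grade 3 or higher AST/ALT or for Hy's law cases, and the Grade 3 or higher events listed for SAR442720 in Section 2.3.1.1 include no transaminase event. The number of participants affected therefore cannot be stated. The conclusion rests on reading a hold until recovery as permission to resume.

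**What to change.** 1. **Section 8.3.6.** Replace the hold-until-recovery sentence with permanent discontinuation of both study drugs, as Appendix 2 and Table 27 already require. Change the trigger to *AST or ALT*, as in Section 4.1.1, Appendix 2 and Table 27.
2. **Table 27, liver row.** State one rule for Grade 3 and one for Grade 4 AST/ALT, by part. If the stop sentence is meant only for certain parts or for recurrence, say so. If it is meant generally, remove the resume text for AST/ALT and align Section 6.6.1.1. Which rule applies is the sponsor's decision.

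The cost is text edits to one sentence and trigger, one table row and possibly Section 6.6.1.1, preferably before Part-3A dosing. No assessment, sample size or analysis changes. The trade-off is clinical: a strict AST/ALT stop loses participants who would have recovered and continued, and a hold-and-resume rule re-exposes them.

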Cardiac toxicities that are considered to be causally related to adagrasib should initially be managed with treatment interruption of adagrasib as outlined in [Table 27](#). Cardiology consultation should be obtained for cases of QTcF prolongation or LVEF decreases falling into the categories indicated in [Table 27](#). In addition, more frequent monitoring of electrolytes that include potassium and magnesium should be considered for participants with vomiting, diarrhea, or past instances of hypokalemia or hypomagnesemia that could recur, and oral and/or intravenous supplementation should be considered for levels below the lower limit of normal. Additionally, arrhythmia should be included in the differential diagnosis of relevant AEs (eg, palpitations, syncope, pre-syncope, or unexplained dyspnea), and unscheduled ECGs should be performed for participants with such events or electrolyte abnormalities as clinically indicated. Additional assessments of LVEF should be performed as clinically indicated at the Investigator's discretion if there are signs or symptoms of cardiotoxicity.

Following resolution of toxicity to the specified degree, dose reduction of adagrasib should be implemented.

Pneumonitis

Pneumonitis has been reported in the Phase 1 study of adagrasib. An evaluation should be performed to assess the attribution of pneumonitis to adagrasib. Pneumonitis considered to be causally related to adagrasib should be initially managed with treatment interruption of adagrasib as outlined in [Table 27](#). Following resolution of toxicity to the specified degree, dose reduction of adagrasib should be implemented.

Other Toxicities

Other toxicities that are considered to be causally related to adagrasib should initially be managed with treatment interruption as outlined in [Table 27](#). Following resolution of toxicity to the specified degree, dose reduction of adagrasib should be implemented.

Hormonal Contraceptives and Thrombotic Events

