10.9 APPENDIX 9: GENERAL GUIDELINES FOR THE MANAGEMENT OF ADVERSE EVENTS

Investigators must be extremely vigilant and be ready to intervene early in the management of AEs, particularly immune-related AEs because the onset of symptoms of irAEs (eg, pneumonitis) may be subtle.

- Detailed guidance for the management of specific AEs (colitis, endocrine AE, pneumonitis, renal AE, dermatologic AE, hepatitis, ophthalmologic AE [uveitis], etc.) is provided in [Table 27](#).
- General guidance is provided in [Table 26](#) below.
- If a participant experiences several AEs which involve different recommendations, the most conservative recommendation should be followed.

The recommendations provided in [Table 26](#) and [Table 27](#) should be seen as guidelines, and the treating physician should exercise clinical judgment based on the symptoms and condition of the individual participant.

Table 26 - General guidelines

Severity	Withhold/restart /discontinue SAR442720 treatment	Withhold/restart/discontinue the combination drug (Pembrolizumab or adagrasib) treatment	Supportive care
Grade 1	No action	No action	Provide symptomatic treatment.
Grade 2	No action	May delay or omit the pembrolizumab dose until Grade ≤ 1 Adagrasib dose modification/ dose interruption per Investigators discretion unless otherwise defined in Table 27 .	Consider systemic corticosteroids (Prednisone 0.5 to 1 mg/kg/day or equivalent) in addition to appropriate symptomatic treatment.
Grade 3	Delay the treatment until toxicity improves to Grade ≤ 1 or baseline.		For any Grade 3-4 immune-related adverse event, if symptoms worsen or do not improve on adequate corticosteroids (prednisone 1 to 2 mg/kg/day or equivalent) within 48 to 72 hours), consider additional immunosuppressive agents (to be selected from agents such as: infliximab, cyclophosphamide, cyclosporine and mycophenolate mofetil). Referral of the participant to a specialized unit for assessment and treatment should be considered.
Grade 4	Permanently discontinue		

Table 27 - Dose modification guidelines for combination regimens (SAR442720 and pembrolizumab combination or SAR442720 and adagrasib combination)

AE	Action

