Skin reactions	
Grade 1 or 2 (tolerable): Administer supportive care and continue study drugs
 
Intolerable Grade 2-Grade 3: Hold both drugs until < Grade 2. If improves to < Grade 2 within 4 weeks, then reduce SAR442720 by one dose level and resume combination drugs at the same dose level.
 
Suspected Stevens-Johnson Syndrome (SJS) or toxic epidermal necrolysis (TEN): Withhold both drugs until adverse reactions recover to Grade 0-1.
 
Grade 4: Hold both drugs until < Grade 1. If improves to < Grade 1 within 4 weeks, resume, reduce SAR442720 by two dose levels and resume combination drugs at the same dose level.
 
Grade 4 or confirmed SJS or TEN: Permanently discontinue both drugs
 
If \geq Grade 3 rash recurs despite two SAR442720 dose level reductions, permanently discontinue both drugs.
 
If rash does not improve within 4 weeks, permanently discontinue both drugs.

Ocular symptoms > Grade 2	
Hold both study drugs and obtain ophthalmology consult.
 
RVO: Any grade, permanently discontinue both drugs (Part-1, 2, and 4 only). In Part-3 permanently discontinue SAR442720 but may continue adagrasib, please consult with the Medical Monitor.
 
Neurosensory retinal detachment: Hold both drugs until resolution to \leq Grade 1. If resolves within 4 weeks, then reduce SAR442720 by one dose level. If visual symptoms > Grade 2 recur despite two dose level reductions, permanently discontinue both drugs. (Part-1, 2 and 4 only). In Part-3 permanently discontinue SAR442720 but may continue adagrasib, please consult with the Medical Monitor.
 
Uveitis/iritis > Grade 2: Hold both study drugs. If resolves to \leq Grade 1 within 4 weeks, then reduce SAR442720 dose by one level and resume both study drugs. If recurs despite two dose level reductions of SAR442720, permanently discontinue both drugs. If > Grade 1 symptoms recur or follow-up ophthalmology examination results worsen, withhold treatment (either SAR442720 and pembrolizumab or SAR442720 and adagrasib) and either further decrease dose or permanently discontinue treatment.
 
Other > Grade 2 AE: Hold SAR442720. If AE doesn't improve within 2 weeks, then consider holding the combination drug. If no improvement within 4 weeks from onset, consider permanently discontinuing both drugs. In ambiguous cases, please consult with the Medical Monitor.

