QTcF prolongation	
Rule out other factors for arrhythmia including myocardial ischemia, electrolyte abnormalities, and concomitant medications. Evaluate concomitant medications that prolong QTcF (eg, 5-HT3 receptor antagonist anti-emetics etc) and discontinue the suspected concomitant medication, as feasible. Hold discontinue both study drugs per below instructions. Consult cardiology.
 
Grade ≥ 3: Hold both study drugs until QTcF < 480 msec; correct electrolytes; consult cardiology. If resolves within 4 weeks, restart both drugs; SAR442720 and adagrasib at one dose level lower (pembrolizumab dose reduction is not allowed); otherwise permanently discontinue.
 
Repeat ECG at 2 weeks and 4 weeks after restarting. Perform additional ECGs monitoring at D15 of each subsequent cycle for 3 cycles then as instructed by the SoA. For recurrence of QTc prolongation follow the guidelines above and reduce dose of SAR442720 and adagrasib by another dose level (pembrolizumab dose reduction is not allowed). Permanently discontinue both SAR442720 and pembrolizumab if after correction of associated risk factors and dose reductions, the QTcF increase meets values of both > 500 msec and > 60 msec change from pre-treatment values.
 
In Part-3: If QTcF Prolongation* > 500 msec and increases by > 60 msec on at least 2 ECGs ≤ 22 days, hold adagrasib until \leq Grade 1 or return to baseline (< 15 msec above baseline). Resume adagrasib at one or two dose levels lower. If QTcF Prolongation* > 500 msec and increases by > 60 msec on at least 2 ECGs > 22 days, discontinue adagrasib.

AE	Action

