Reduction in LVEF and other cardiac toxicities	
Asymptomatic reduction: absolute decrease in LVEF \geq 20% from baseline and below LLN, withhold treatment (either SAR442720 and pembrolizumab or SAR442720 and adagrasib) for up to 4 weeks and repeat echocardiogram (ECHO) for LVEF at 2, 4, 10, and 16 weeks after hold. Restart at reduced dose if LVEF \geq LLN and absolute decrease from baseline LVEF $<$ 20%. Permanently discontinue if symptoms of heart failure are present.
 
Symptomatic reduction: In case of symptomatic systolic dysfunction with an LVEF decrease from baseline \geq 10% and/or below LLN, withhold both SAR442720 and pembrolizumab for up to 4 weeks and consider permanent discontinuation if considered causative; in Part-3 permanently discontinue SAR442720 and adagrasib. Consult cardiology and the Medical Monitor.
 
If reinitiating treatment, ALL of the following must be present: an EF decrease not considered to be associated with the study drug, symptoms resolve, LVEF $>$ LLN, and absolute decline from baseline was $<$ 10%; otherwise, permanently discontinue both drugs.
 
If reinitiating treatment, restart both study drugs, SAR442720 and adagrasib at a lower dose (pembrolizumab dose reduction is not allowed). Please consult with the Medical Monitor for individual cases.
 
All participants who require dose reduction of SAR442720 due to treatment related systolic dysfunction should have ECHO at 2 weeks, 4 weeks, 10 and 16 weeks, then per protocol or as clinically indicated.
 
In Part-3:
 
For all other Grade \geq 3 cardiac toxicities/adverse drug reactions hold study treatment until recovery to \leq Grade 1 or to baseline. Adagrasib/SAR442720 treatment may resume at one dose level lower. For QTc prolongation please refer to the previous bullet. Please consult with the Medical Monitor for individual cases.

Hypertension	
Grade 2: Treat according to institutional guidelines with goals blood pressure $<$ Grade 1. Continue both drugs.
 
Grade 3: Treat according to institutional guidelines with goal blood pressure $<$ Grade 1. Consider holding SAR442720 and continue pembrolizumab and adagrasib. If improved restart SAR442720 at reduced dose level.
 
Grade 4: Treat according to institutional guidelines. Discontinue both SAR442720 and pembrolizumab. In Part-3 hold adagrasib until \leq Grade 1 or baseline, then may resume one dose level lower.

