Other non-hematologic AEs	
Intolerable Grade 2 or Grade 3: Hold both drugs until \leq Grade 1. If improves within 4 weeks, then resume pembrolizumab at same dose and dose reduce SAR442720 in Part-1, 2, 4. In Part-3 dose reduce both SAR442720 and adagrasib; if not resolved to \leq Grade 1 within 4 weeks, permanently discontinue both drugs (SAR442720 and pembrolizumab or SAR442720 and adagrasib). If event recurs, hold both drugs and consider dose reduction the drug not previously dose reduced upon improvement \leq Grade 1.
 
Grade 4: Consider permanent discontinuation both drugs. Otherwise, discuss with sponsor Medical Monitor and hold both drugs until \leq Grade 1, if improves within 4 weeks, then consider resuming pembrolizumab, and both SAR442720 and adagrasib with dose reduction (pembrolizumab dose reduction is not allowed). Of SAR442720. For recurrent Grade 4 AE, permanently discontinue both drugs.
 
Based on the investigator's assessment of the AE, either one, both SAR442720 and pembrolizumab or SAR442720 and adagrasib may be held if a clear attribution may be established.
 
Grade \geq3 non hematological laboratory abnormalities if clear attribution may be established hold both drugs, upon improvement to \leq Grade 1 resume SAR442720 and adagrasib lower dose level; resume pembrolizumab same dose level. Grade \geq3 non hematological laboratory abnormalities if clear attribution may be established hold both drugs, upon improvement to \leq Grade 1 resume SAR442720 and adagrasib lower dose level; resume pembrolizumab at same dose level.

Nephritis	
Grade 2 with creatinine >1.5 to ≤ 3 times upper limit of normal (ULN): In Part-1, 2, and 4 continue SAR442720 and withhold pembrolizumab until adverse reactions recover to Grade 0 to 1. In Part-3, continue SAR442720 and consider continuing adagrasib at the same dose level or one dose level lower.
 
Grade \geq3 with creatinine >3 times ULN: Permanently discontinue pembrolizumab. In Part-3, if Grade \geq3 creatinine increased \leq 22 days hold adagrasib until \leq Grade 1 or return to baseline, then adagrasib treatment may resume at the same dose level or one dose level lower. For Grade \geq3 creatinine increased $>$ 22 days discontinue adagrasib. Action taken with SAR442720 should be discussed with Medical Monitor depending on the clinical case.

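### In Table 27's QTcF row the general line restarts adagrasib and the Part-3 line stops it for the same narrow class of event, and no text says which line prevails

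*Protocol*

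**What the plan says.** The QTcF row of Table 27 (protocol Section 10.9) holds two sets of instructions that bear on adagrasib.

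- **General line, Grade 3 or worse.** Both drugs are held until QTcF is below 480 msec. Then: "If resolves within 4 weeks, restart both drugs; SAR442720 and adagrasib at one dose level lower". If the event does not resolve in that time, treatment stops for good. The line carries no Part restriction.
- **Part-3 line.** It applies when QTcF is above 500 msec with a rise of more than 60 msec on at least two ECGs. Up to 22 days, adagrasib is held until Grade 1 or lower, or until QTcF is less than 15 msec above baseline; it then resumes one or two dose levels lower. Past the greater-than sign, the longer case reads "22 days, discontinue adagrasib".

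Three other places touch on the question.

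- The introduction to Appendix 9 has a tie-break: "If a participant experiences several AEs which involve different recommendations, the most conservative recommendation should be followed". It also describes Tables 26 and 27 as guidelines to be applied with clinical judgment.
- Section 6.6.1.1 says that once adagrasib has been withheld for at least 22 "consecutive days, then permanent discontinuation from treatment with one or both agents should be considered". Its cardiac paragraph says: "Following resolution of toxicity to the specified degree, dose reduction of adagrasib should be implemented".
- The next row of Table 27, on LVEF and other cardiac toxicities, says: "For QTc prolongation please refer to the previous bullet".

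**The concern.** A dose-modification table should give a site one instruction for one event. Here a participant with marked and persistent QTcF prolongation could be put back on adagrasib under one line and taken off it under another line of the same row. Two sites could act in opposite ways and each point to the text.

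The drug matters. Section 2.3.1.4 lists QT prolongation among the commonly reported events attributed to adagrasib, and Section 2.3.1.5 does not exclude a higher frequency with the combination. What is at stake is participant safety and consistent conduct in Part-3, not the statistical analysis.

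**Working it through.** The plan gives no figure to reproduce. The check is a comparison of texts, with simple arithmetic on the two periods.

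**1. Does the general line reach Part-3?** Yes. It names adagrasib, which the synopsis lists as a Part-3 drug only. Other rows separate the Parts: the retinal vein occlusion rule is marked as applying to Parts 1, 2 and 4 before its own Part-3 rule, and the hemorrhage and hepatitis rows also separate them. The general QTcF line does not.

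**2. Does the Part-3 event fall under the general line?** Yes. Section 4.1.1 describes Grade 3 QTcF prolongation as above 450 msec or a change above 50 msec. An event above 500 msec with a rise above 60 msec exceeds both.

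**3. Side by side, for adagrasib, with both periods counted from the same day:**

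| Event resolves | General line | Part-3 line |
|---|---|---|
| By day 22 | Restart below 480 msec, one level lower | Resume at Grade 1 or lower, or less than 15 msec above baseline, one or two levels lower |
| Days 23 to 28 | Restart, one level lower | Discontinue |
| After day 28 | Discontinue | Discontinue |

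Four weeks = 28 days, and 28 − 22 = 6 days of direct conflict.

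**4. A constructed case (assumed values).** Onset and hold are both day 0, and baseline is 430 msec. QTcF is 510 msec on days 0 and 23: 510 > 500, 510 − 430 = 80 > 60, two ECGs, and 23 > 22. QTcF is 475 msec on day 27: 475 < 480 and 27 ≤ 28. The general line restarts adagrasib; the Part-3 line discontinues it.

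**5. Shorter events.** Suppose the 475 msec reading came by day 22. The general line's threshold is met. The reading is 475 − 430 = 45 msec above baseline, not under 15, and it is still above the 450 msec in Section 4.1.1's description of Grade 3. The Part-3 line therefore keeps the hold. Both lines end in a restart, but at different times and possibly at different doses.

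**6. Dependence on the start point.** The QTcF row gives none. The ocular row of the same table does for one of its rules: "If no improvement within 4 weeks from onset, consider permanently discontinuing both drugs". Let h be the days from onset to hold.

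- Both periods from onset, or both from the hold: 6 days.
- 22 days from onset, 4 weeks from the hold: 28 + h − 22 = 6 + h days.
- 22 days from the hold, 4 weeks from onset: max(0, 6 − h) days, which is zero once h reaches 6.

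The documents give no value for h.

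**7. Is precedence stated anywhere?** No. The Appendix 9 tie-break is worded for several adverse events, not for one event with two instructions. The cardiac paragraph of Section 6.6.1.1 relies on Table 27, and the LVEF row points back to the QTcF row.

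**The case against.** The strongest answer is that the row's layout already implies the result. General text comes first, followed by a labelled Part-3 paragraph with narrower criteria and adagrasib-only instructions. The general line still has work to do in Part-3, for SAR442720 and for Grade 3 or worse events outside those criteria. The Nephritis row uses the same cut for adagrasib (past 22 days it reads "22 days discontinue adagrasib") with no competing four-week restart, which supports treating the Part-3 text as the adagrasib rule. Table 27 is guidance, the QTcF row calls for a cardiology consult, and the LVEF row, straight after its QTc cross-reference, offers Medical Monitor review of individual cases. Section 7.1.1 separately allows therapy to stop when QTcF prolongation does not resolve.

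All of this stands. It makes a wrong restart less likely and keeps the point small. It does not supply the missing precedence, which the reader must infer.

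A reader might also infer a three-way conflict that includes Section 6.6.1.1. The documents do not support that. Advice to consider discontinuation after a long hold does not contradict a rule that requires it, and the cardiac paragraph defers to Table 27.

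The meaning of the 22 days is also open: event duration, days withheld or ECG spacing. The Part-3 line marks its term with an asterisk whose footnote is not visible in the text available here, and that footnote might define it.

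**Conclusion.** The inconsistency is real and narrow. For adagrasib in Part-3, two lines of one row give opposite instructions for events resolving on about days 23 to 28, and different thresholds and reductions for events of 22 days or less. The six-day figure assumes that the 22 days are event duration and that both periods share a start point; under mixed start points the window can widen or close.

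The number of participants affected cannot be estimated. A reader might apply the 10.8% any-grade, adagrasib-attributed QT rate in Section 2.3.1.4 to Part-3: (15 to 30) + 40 = 55 to 70 participants, times 0.108, is 5.9 to 7.6. That counts any QT prolongation. The documents give no rate for the much smaller group above 500 msec, with a rise above 60 msec, for more than 22 days.

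A reader might also infer that the MTD or the response analysis is at risk. It is not. Grade 3 QTcF prolongation related to treatment in Cycle 1 is already a DLT under Section 4.1.1, whatever is done afterwards, and the ORR definition and analysis population do not depend on which line a site follows.

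**What to change.** Add one sentence to the QTcF row of Table 27:

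> In Part-3, for QTcF >500 msec with a >60 msec rise on at least 2 ECGs, the Part-3 paragraph governs adagrasib; the general 4-week adagrasib restart applies only to other Grade ≥3 QTcF events.

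This adopts the protocol's own more specific and more cautious rule, and it also settles the difference for events of 22 days or less.

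The sponsor should choose and state the start point of the 22-day and 4-week periods. The documents do not favor event onset: the only 22-day period for adagrasib with a stated basis, in Section 6.6.1.1, counts days withheld. Scheduled Part-3 ECGs (Table 4: C1D1, C1D15, then every two cycles from C3) may also miss the true onset.

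The cost is a line of text in one table row, with no added visits, procedures or participants.
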